6.4.2 Secondary Efficacy Endpoints

The secondary efficacy endpoints for this study are as follows:

- *Time to alleviation or improvement of COVID-19 symptoms (Items 1–12 of the COVID-19 Symptom Diary) maintained for a duration of 43 hours, defined as follows:*
 - *For new symptoms: time from randomization to the alleviation of COVID-19 symptoms (i.e., a score of 0 [none] or 1 [mild] on the COVID-19 Symptom Diary)*
 - *For preexisting symptoms: time from randomization to when a patient's symptoms have been maintained or improved (Note: Improved requires at least a single category improvement from baseline on the COVID-19 Symptom Diary Likert scale.)*
- Time to alleviation of COVID-19 symptoms defined as the time from randomization to the point at which the following criterion is met and maintained for at least 21.5 hours:
 - Score of 0 or 1 for Items 1–12 of the COVID-19 Symptom Diary
- *Time to alleviation of COVID-19 symptoms defined as the time from randomization to the point at which the following criterion is met and maintained for at least 43 hours:*
 - *Score of 0 or 1 for Items 1–12 of the COVID-19 Symptom Diary*
- Time to one-category improvement of baseline presenting COVID-19 symptoms (*Items 1–12 of the COVID-19 Symptom Diary*) maintained for a duration of 21.5 hours defined as time from randomization to when the symptoms have improved by at least one category from baseline on the *COVID-19 Symptom Diary Likert scale*
- Time to alleviation of individual symptoms, defined as the time from randomization to the point at which the following criterion is met and maintained (for each individual symptom) for at least 21.5 hours:
 - Score of 0 or 1 for Items 1–14 of the COVID-19 Symptom Diary
- Proportion of patients requiring hospitalization for COVID-19

- Proportion of patients with ≥ 1 COVID-19 related medically attended visit through to study end (defined as hospitalization, ER visit, urgent care visit, physician's office visit, or telemedicine visit, with the primary reason for the visit being COVID-19) (see Section 4.5.6.3 for assessments to be done at weekly visits)
- Duration of fever (time to return to afebrile state [temperature $\leq 37.5^{\circ}\text{C}$] and remaining so for at least 21.5 hours) (see Section 6.4.1)
- Frequency of COVID-19 related complications (e.g., death, hospitalization, radiologically confirmed pneumonia, acute respiratory failure, sepsis, coagulopathy, pericarditis/myocarditis, cardiac failure)

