Key Secondary: Time to one-category improvement of symptoms	Time from randomization to one-category improvement of baseline presenting COVID-19 symptoms maintained for a duration of 21.5 hours, right censored at day 29 if the patient doesn't meet criteria	Treatment-policy strategy approach will be taken. Patients are followed, assessed and analyzed irrespective of their completion of the planned course of the study treatment and irrespective of rescue and concomitant therapy (contd.)	Hypothetical approach where patient censored at Day 29 if intercurrent event prior to achieving the endpoint (contd.)	Hazard ratio (contd.)	Patient censored at Day 29 if study withdrawal is prior to achieving the endpoint (contd.)
Secondary: Time to alleviation of individual symptoms	Time from randomization to alleviation an individual COVID-19 symptoms maintained for a duration of 21.5 hours, right censored at day 29 if the patient doesn't meet criteria				
Secondary: Time to return to afebrile state [temperature \leq 37.5C]	Time from randomization to return to afebrile state [temperature \leq 37.5C] maintained for a duration of 21.5 hours for a patient with fever at baseline, right censored at day 29 if the patient doesn't meet criteria				
Secondary: Proportion of patients requiring hospitalization for COVID-19	Patients requiring hospitalization for COVID-19 through to study end (including early termination visits)		Composite strategy where patient considered as having the event if they die	Difference in proportion of patients between treatments	The outcome measure up to point of study withdrawal will be used

Table 2 Estimands (cont.)

Endpoint	Variable or Outcome measurement	Intercurrent Events		Population-Level Summary for the Variable	Handling of Missing Data Study Withdrawal/ Lost to Follow-Up
		Treatment Withdrawal/ Rescue/ Concomitant Medications	Death		

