5.3.1 Definition of Primary Endpoint

The time to alleviation or improvement of COVID-19 symptoms is defined as the time from randomization to the first time at which all COVID-19 symptoms from Items 1-12 of the COVID-19 Symptom Diary were either alleviated, maintained or improved for a minimum duration of 21.5 hours (24 hours minus 10%, to allow some flexibility in the timing of assessments). Alleviation, maintenance, or improvement of symptoms is defined as the time when all 12 COVID-19 symptoms from Items 1-12 of the COVID-19 Symptom Diary have been assessed by the patient as follows:

- For pre-existing symptoms (i.e., symptoms that existed prior to developing COVID-19) judged by the patient to be worse at screening:
 - Improvement of at least one grade on the Likert scale from baseline if the severity at baseline is graded moderate or severe:
 - Severe to moderate, mild, or none
 - Moderate to mild or none
 - Mild to mild or none
 - None to mild or none

Note: At screening, patients will only be asked if preexisting symptoms existed (within the last 30 days) and if they were worsened by COVID-19. Patients will be asked to rate the severity at baseline that needs to improve. To avoid recall bias, patients will not be asked to rate the severity of preexisting symptoms prior to COVID-19.

- For pre-existing symptoms (i.e., symptoms that existed prior to developing COVID-19) judged by the patient NOT to be worse at screening:
 - Maintained (no worsening) baseline severity if the severity at baseline is graded moderate or severe:
 - Severe to severe, moderate, mild, or none
 - Moderate to moderate, mild or none
 - Mild to mild or none
 - None to mild or none
- For new symptoms (i.e., symptoms that develop due to COVID-19 which present prior to or post baseline):
 - Alleviation of COVID-19 symptoms (i.e., a score of 0 [none] or 1 [mild] on the COVID-19 Symptom Diary):
 - Severe to mild, or none
 - Moderate to mild, or none
 - Mild to mild or none
 - None to mild or none

Where the baseline assessment for COVID-19 symptom severity is missing, the COVID-19 symptoms for a patient will be treated as new symptoms and therefore must meet the alleviation criteria even if symptoms had been identified as existing prior to developing COVID-19.

The primary endpoint will be tested using a two-sided significance level of 0.025.

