5.4.1.4 Time to One-Category Improvement of Baseline Presenting Symptoms Maintained for 21.5 Hours

Time to one-category improvement of baseline presenting COVID-19 for Items 1-12 of the COVID-19 Symptom Diary maintained for a duration of 21.5 hours defined as time from randomization to when the symptoms have improved by at least one category from baseline on the Likert scale, where improvement is defined as:

- For pre-existing symptoms (i.e., symptoms that existed prior to developing COVID-19) judged by the patient to be worse at screening OR for new symptoms (i.e., symptoms that develop due COVID-19 which present prior to or post baseline):
 - Improvement of at least one grade on the Likert scale from baseline if the severity at baseline is graded moderate or severe:
 - Severe to moderate, mild, or none
 - Moderate to mild or none
 - Mild to mild or none
 - None to mild or none
- For pre-existing symptoms (i.e., symptoms that existed prior to developing COVID-19) judged by the patient NOT to be worse at screening:
 - Maintained (no worsening) baseline severity:
 - Severe to severe, moderate, mild, or none
 - Moderate to moderate, mild or none
 - Mild to mild or none
 - None to none

Where the baseline assessment for COVID-19 symptom severity is missing, the patient will be excluded from the analysis.

The same statistical methods as for the primary endpoint will be used as described in Section 5.3.2.

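### The key secondary on one-category improvement counts a new or worsened symptom as improved when it stays mild, or even goes from none to mild

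*SAP*

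**What the plan says.** Protocol 6.4.2 defines the endpoint for Items 1–12, held for 21.5 hours, as "time from randomization to when the symptoms have improved by at least one category from baseline". It makes no exception for mild symptoms. SAP Table 1 uses the same definition. SAP Table 2 lists the endpoint as a key secondary, with the variable "Time from randomization to one-category improvement of baseline presenting COVID-19 symptoms maintained for a duration of 21.5 hours".

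SAP 5.4.1.4 starts from the same place, "time from randomization to when the symptoms have improved by at least one category from baseline on the Likert scale, where improvement is defined as", and then lists the accepted transitions:

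- **New symptoms, and pre-existing symptoms judged worse at screening:** "Improvement of at least one grade on the Likert scale from baseline if the severity at baseline is graded moderate or severe". Below that condition come the rows "Mild to mild or none" and "None to mild or none". New symptoms here include those that first appear after baseline.
- **Pre-existing symptoms judged not worse:** baseline severity need only be maintained, and an item scored none must stay none.
- **Missing baseline severity:** the patient is excluded.

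For the primary endpoint, SAP 5.3.1 asks of new symptoms, at every baseline grade: "Alleviation of COVID-19 symptoms (i.e., a score of 0 [none] or 1 [mild] on the COVID-19 Symptom Diary". Where baseline severity is missing, it keeps the patient and treats the symptoms as new.

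SAP Appendix 1 lists three changes from the protocol's planned analyses. The scoring of this endpoint is not among them.

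**The concern.** The defining sentence and the scoring list disagree. Under the sentence, a presenting symptom rated mild has to reach none. Under the list it may stay where it is, and an item scored none may become mild.

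The endpoint belongs to the key secondary set, which SAP 2.2 places under multiplicity control, so a significant result could be claimed as confirmatory. Under its present name, readers would take the result to mean that presenting symptoms had improved by a category, although every mild one might be unchanged. Clearance of residual mild symptoms is also the main thing a literal one-category endpoint would add to the primary, and this scoring removes it.

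**Working it through.** The plan states no figure on this point, so the check compares rules. Inputs are the diary scale (0 none, 1 mild, 2 moderate, 3 severe; SAP Appendix 2) and the accepted transitions in SAP 5.4.1.4 and 5.3.1.

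**Step 1. Accepted post-baseline scores, by symptom class and baseline grade.**

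| Class | Baseline | Literal one-grade drop | Key secondary (5.4.1.4) | Primary (5.3.1) | Key secondary = primary? |
|---|---|---|---|---|---|
| New | 3 | 0, 1, 2 | 0, 1, 2 | 0, 1 | no (looser) |
| New | 2 | 0, 1 | 0, 1 | 0, 1 | yes |
| New | 1 | 0 | 0, 1 | 0, 1 | yes |
| New | 0 | impossible | 0, 1 | 0, 1 | yes |
| Pre-existing, worse | 3 | 0, 1, 2 | 0, 1, 2 | 0, 1, 2 | yes |
| Pre-existing, worse | 2 | 0, 1 | 0, 1 | 0, 1 | yes |
| Pre-existing, worse | 1 | 0 | 0, 1 | 0, 1 | yes |
| Pre-existing, worse | 0 | impossible | 0, 1 | 0, 1 | yes |
| Pre-existing, not worse | 3 | not required | 0–3 | 0–3 | yes |
| Pre-existing, not worse | 2 | not required | 0–2 | 0–2 | yes |
| Pre-existing, not worse | 1 | not required | 0, 1 | 0, 1 | yes |
| Pre-existing, not worse | 0 | not required | 0 | 0, 1 | no (stricter) |

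**Step 2. Credit without a one-grade drop.** For new and worsened symptoms this arises at baseline mild (score 1 accepted) and baseline none (scores 0 and 1 accepted). It does not arise at moderate or severe.

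**Step 3. One patient.** Take three new symptoms at moderate, four new at mild and five items at none. Suppose the three fall to mild, the four do not move, and this holds for 21.5 hours. SAP 5.4.1.4 records an event, and would still do so if one of the five items had gone from none to mild. Under Protocol 6.4.2 there is no event, because four presenting symptoms have not improved.

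**Step 4. Overlap with the primary.** The cells that match number 12 − 2 = 10. The exceptions are new symptoms severe at baseline and not-worse pre-existing symptoms scored none. Handling of a missing baseline also differs. A patient with a recorded baseline, only new symptoms and none severe touches none of these exceptions, so the two event times are the same.

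**Step 5. How many patients that is.** The documents do not say. Entry requires at least three symptoms scoring 2 or more (Protocol 4.1.1), but the split between moderate and severe is not given. As an assumption only, suppose a patient has m new symptoms scoring 2 or more, each severe with probability s, independently. The share with no severe symptom is (1 − s)^m:

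- m = 3: 0.95³ = 86% at s = 5%; 0.80³ = 51% at s = 20%; 0.50³ = 13% at s = 50%.
- m = 7: 0.95⁷ = 70%; 0.80⁷ = 21%; 0.50⁷ = 1%.

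The range is too wide to support a statement about the typical patient.

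**Step 6. Effect of a literal rule.** Requiring mild to reach none changes two cells (new and worsened, baseline mild), leaving 10 − 2 = 8 that match the primary. Taking items scored none out of the requirement changes two more (new and worsened, baseline none), leaving 8 − 2 = 6.

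**The case against.** The best defence is that the scoring is explicit and pre-specified. The protocol leaves detailed specification to the SAP, and 5.4.1.4 says what it means by improvement. Mild is treated as an acceptable state throughout the plan: alleviation is a score of 0 or 1, entry needs scores of 2 or more, and the worked example of a one-grade improvement in Protocol 6.4.1 covers only severe and moderate symptoms. The term baseline presenting is never defined. If it means moderate or severe at baseline, the mild row serves only as a guard against worsening.

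The consistency argument has some force, and it is a reason to let the sponsor keep the scoring under another name. The reading of the term does not fit the SAP:

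- SAP 5.7.2.2 lists the number of symptoms present at baseline separately from the number scoring 2 or more.
- SAP 5.4.2.2 states a threshold of 2 or more when it wants one.
- The row from none to mild allows worsening, so the rows are not a guard against it.
- The moderate-or-severe limit makes sense in the primary, where mild is the success level, but not in an endpoint defined by a one-category drop.

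Two stronger readings are tempting, and the documents support neither. A reader might infer that the endpoint equals the primary for most patients. That depends on how common severe new symptoms are, which is not given, and it overlooks the stricter none-to-none row and the missing-baseline rule. A reader might also infer that the overlap inflates type I error. It does not: under SAP 2.2 the key secondaries are gated behind the primary. Overlap between endpoints is not an error in itself, and the same rule applies to both arms.

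**Conclusion.** The contradiction is established from the text alone and needs no assumption about symptom frequencies. For new and worsened symptoms, SAP 5.4.1.4 credits no change from mild, and a change from none to mild, as one-category improvement. This is against Protocol 6.4.2, SAP Table 1 and the section's own opening sentence, and it is not declared in Appendix 1.

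The consequence is a confirmatory endpoint whose name claims more than its scoring delivers, and which adds limited evidence beyond the primary. How limited cannot be quantified from the documents. The maintenance rule for pre-existing symptoms judged not worse is a separate choice and is not questioned here.

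**What to change.** Before unblinding, amend SAP 5.4.1.4 as follows:

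1. Define baseline presenting as items scored 1 or more at baseline. SAP 5.3.3 uses the same term for a sensitivity analysis of the primary, so one definition should serve both.
2. For presenting symptoms that are new or judged worse, require a drop of at least one grade: severe to moderate or lower, moderate to mild or none, mild to none.
3. Take items scored none at baseline, and symptoms arising after baseline, out of the improvement requirement. Deleting the moderate-or-severe condition alone would not be enough, because it would demand an improvement from none. If a guard against new symptoms is wanted, state it as a separate condition.

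The cost is SAP wording and one derivation change. Requiring mild to reach none can only delay or remove events, while releasing items scored none can only bring events forward. The likely downside is somewhat fewer or later events on this endpoint; the documents do not allow a figure.

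If the sponsor prefers the present scoring, rename the endpoint in Tables 1 and 2, section 5.4.1.4 and Figure 2, so that no one-category improvement is claimed for mild symptoms, and list the change in Appendix 1. That costs wording only.

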5.4.1.5 Time to Cessation of SARS-CoV-2 Viral Shedding as Measured by RT-qPCR

Time to cessation of viral shedding by RT-PCR is defined as the time from randomization to the first time when a negative qualitative virus RNA by RT-PCR test result is obtained. The same statistical methods as for the primary endpoint will be used as described in Section 5.3.2.

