Key Secondary (Virology): Time to cessation of SARS-CoV-2 viral shedding, as measured by RT-qPCR	Time from randomization to cessation of SARS-CoV-2 viral shedding, right censored at Day 14 if the patient doesn't meet criteria		Hypothetical approach where patient censored at Day 14 if the patient doesn't meet criteria if intercurrent event prior to achieving the endpoint	Hazard ratio	Patient censored at Day 14 if the patient doesn't meet criteria if study withdrawal is prior to achieving the endpoint
Secondary (Virology): Proportion of patients positive for SARS-CoV-2 virus RNA	Patients who are positive for SARS-CoV-2 virus RNA, as measured by RT-qPCR at Day 3, Day 5, Day 7 and Day 14		While on treatment approach where the outcome measure up to point of intercurrent event will be used	Difference in proportion of patients between treatments	The outcome measure up to point of study withdrawal will be used

Table 2 Estimands (cont.)

Endpoint	Variable or Outcome Measurement	Intercurrent Events		Population-Level Summary for the Variable	Handling of Missing Data
		Treatment Withdrawal/Rescue/Concomitant Medications	Death		
Secondary (Safety): Incidence of adverse events	Patients with an adverse event			Proportion of patients for each treatment	
Secondary (Safety): Severity of adverse events	Severity of adverse events determined according to NCI CTCAE v5.0	Treatment-policy strategy approach will be taken. Patients are followed, assessed and analyzed irrespective of their completion of the planned course of the study treatment and irrespective of rescue and concomitant therapy.	Not an intercurrent event as it is the outcome measure	Proportion of patients for each treatment for each severity grade	
Secondary (Safety): Incidence of serious adverse events	Patients with a serious adverse event			Proportion of patients for each treatment	The outcome measure up to point of study withdrawal will be used (contd.)
Secondary (Safety): Change from baseline in vital signs	Vital signs, including SpO2		While on treatment approach where the outcome measure up to point of intercurrent event will be used	Means for each treatment	
Secondary (Safety): Change from baseline in targeted laboratory results	Targeted laboratory results				

Table 2 Estimands (cont.)

Endpoint	Variable or Outcome Measurement	Intercurrent Events		Population-Level Summary for the Variable	Handling of Missing Data
		Treatment Withdrawal/Rescue/Concomitant Medications	Death		

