4. ANALYSIS SETS

The following analysis sets are defined:

Analysis Set	Definition
Efficacy-evaluable	All randomized patients who received at least one dose of study treatment and were centrally assessed as reverse transcriptase quantitative polymerase chain reaction (RT-qPCR) positive for SARS-CoV-2 (by nasopharyngeal swab) at any point during the study, with patients grouped according to randomized treatment.
All patients	All randomized patients, with patients grouped according to randomized treatment.
Safety-evaluable	All randomized patients who received at least one dose of study treatment, with patients grouped to placebo if all doses received were placebo and to AT-527 if at least one dose of AT-527 was received.
PK-evaluable	All randomized patients who received at least one dose of study treatment and have sufficient data to enable estimation of key parameters (e.g., maximum concentration [C_{max}] and minimum concentration [C_{min}]), with patients grouped according to treatment received.

PK=pharmacokinetic; RT-qPCR= reverse transcriptase quantitative polymerase chain reaction; SARS-CoV-2=severe acute respiratory syndrome coronavirus-2.

The efficacy-evaluable set will be used for the primary efficacy analysis. In addition to having been randomized, patients are also required to have received at least one dose of study treatment, so that patients who drop out of the study after randomization but prior to first dose of study treatment will not be included in the analysis. As this is a double-blind study, patients will not know their randomized treatment therefore this cannot influence their decision to take study treatment. Additionally, patients are also required to be centrally assessed as RT-qPCR positive for SARS-CoV-2 (by nasopharyngeal swab) at any point during the study. This cannot be required prior to randomization as this would extend the time between first symptom onset and first dose of study treatment.

In addition, data will be listed for patients who do not receive the treatment they are assigned to at any timepoint.

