5.1 GENERAL CONSIDERATION

All statistical tests will be performed at a 0.025 significance level using two-sided tests, unless otherwise noted. As specified in Section 2.2, key secondary endpoints for which the multiplicity-adjusted p-value is greater than 0.025 will not be considered statistically significant. These endpoints and all endpoints not under multiplicity control will be considered to provide supportive information.

Statistical tests will use stratification factors according to IxRS unless there is considerable imbalance in IxRS and electronic Case Report Form (eCRF) stratum classification. Stratification factors may need to be removed or have their levels combined so that low or zero counts in one stratum do not invalidate relevant statistical tests.

Unless otherwise specified, continuous variables will be summarized by using the number of non-missing observations, arithmetic mean, standard deviation (SD), median, minimum, and maximum values as summary statistics; categorical variables will be summarized by using the frequency count and the percentage of subjects in each category as summary statistics. Descriptive summaries will be tabulated by treatment group.

All efficacy and virology analyses will be performed on the efficacy-evaluable set, all patient disposition and study conduct analyses will be performed on the All Patients set, and all safety analyses will be performed on the safety-evaluable set, unless otherwise specified.

Missing data due to study withdrawal or lost to follow up will be handled as described in Table 2. Any other missing data will not be imputed unless otherwise specified in the specific section describing an endpoint.

Time to event secondary efficacy and virology endpoints will use the same statistical methods as used for the primary endpoint as described in Section 5.3.2, and will be measured in days unless otherwise stated.

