where t_k (hours) represents the date of the k^{th} virus RNA (reverse-transcriptase polymerase chain reaction [RT-PCR]) assessment ($k = 0, \dots, K$) and y_k represents the \log_{10} value of the k^{th} virus RNA (RT-PCR) assessment. 24-hours of time will be converted into one day.

Descriptive summary statistics of the AUC will be presented for each treatment group along with the p-value from the van Elteren test.

All secondary virology endpoints will be evaluated on the nasopharyngeal swab samples. Additional descriptive analyses for saliva and serum samples will be performed on an exploratory basis for the secondary virology endpoints, as required.

The qualitative result of the SARS-CoV-2 reverse-transcriptase polymerase chain reaction (RT-PCR) test is determined using cycle threshold (Ct) values. If the qualitative result is positive, then an associated quantitative result is also provided. The quantitative result is either numerical or below the limit of quantification (BLQ). The limit of quantification (LOQ) for the virus RNA is 120 copies/ml. If the virus RNA sample has a

positive qualitative result, but a quantitative result BLQ, virus RNA will be imputed as LOQ – 1 (119 copies/mL). Negative qualitative samples will be imputed as LOQ/2 (60 copies/ml) before being transformed to the log10 scale.

Baseline is defined as the last available assessment prior to first dose of study treatment. For efficacy analyses, if there is no such assessment available then baseline can be up to 4 hours post first dose, with the earliest assessment used as baseline in the case of multiple assessments within this time.

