Time to alleviation of individual symptoms (Items 1-14 of the COVID-19 Symptom Diary) is defined separately for each symptom as the time from randomization to the point at which a score of 0 or 1 for the individual symptom is met and maintained for at least 21.5 hours in patients with a symptom score ≥ 2 at baseline. The endpoints corresponding to each of the symptoms are as follows:

- Time to alleviation of nasal congestion or runny nose
- Time to alleviation of sore throat
- Time to alleviation of cough
- Time to alleviation of shortness of breath
- Time to alleviation of muscle or body aches
- Time to alleviation of fatigue
- Time to alleviation of headache
- Time to alleviation of chills/sweats
- Time to alleviation of feeling hot or feverish

- Time to alleviation of nausea
- Time to alleviation of vomiting
- Time to alleviation of diarrhea
- Time to alleviation of sense of smell
- Time to alleviation of sense of taste

The same statistical methods as for the primary endpoint will be used as described in Section [5.3.2](#).

Where a baseline assessment for COVID-19 symptom severity is missing for an individual symptom, the patient will be excluded from the analysis.

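### Time to cessation of viral shedding can be scored before a patient's first central positive swab, because no earlier central positive is required

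*SAP*

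**What the plan says.** SAP 5.4.1.5 sets the event as "the time from randomization to the first time when a negative qualitative virus RNA by RT-PCR test result is obtained". The matching row of SAP Table 2 reads "Time from randomization to cessation of SARS-CoV-2 viral shedding, right censored at Day 14 if the patient doesn't meet criteria" and adds no condition on baseline status.

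On the analysis set, SAP 5.1 states "All efficacy and virology analyses will be performed on the efficacy-evaluable set" unless otherwise specified, and 5.4.1.5 specifies nothing else. SAP 4 admits dosed, randomized patients who were "centrally assessed as reverse transcriptase quantitative polymerase chain reaction (RT-qPCR) positive for SARS-CoV-2 (by nasopharyngeal swab) at any point during the study". It explains that central positivity cannot be a condition of randomization, because waiting for it would delay treatment.

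On samples, SAP 5.1 states "All secondary virology endpoints will be evaluated on the nasopharyngeal swab samples". Protocol Appendix 1 schedules nasopharyngeal swabs on Days 1, 3, 5, 7 and 14, with the Day 1 swab before dosing. Protocol 3.1 has patients randomized on or before Day 1.

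On entry, Protocol 4.1.1 requires a positive RT-PCR or validated rapid antigen test no more than 72 hours before randomization. Appendix 1 shows that this test is run locally.

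**The concern.** Time to cessation has meaning only for someone shown to be shedding by the assay that dates the cessation. Here a patient can enter the set through a Day 5 swab and already carry an event from Day 3. That date comes before the only evidence that qualified the patient.

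Elsewhere the SAP writes the missing condition out. Individual-symptom alleviation (5.4.2.2) is assessed "in patients with a symptom score" of at least 2 at baseline. Return to afebrile state (5.4.2.5) is limited to patients febrile at baseline. Both exclude patients whose baseline is missing. The shedding endpoint has no such rule.

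Two things are at stake. The endpoint is under multiplicity control (SAP 2.2), so its event rule should be unambiguous before unblinding. Premature events also dilute the comparison, and because late conversion may itself respond to an antiviral, they need not be balanced between arms.

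**Working it through.** **1. The plan's own figure.** The documents give no power or event figure for shedding. The design inputs reproduce for the primary endpoint: (2.241 + 1.282)² / [(2/3)(1/3)(ln 1.25)²] = 1122 events, as SAP 3 states.

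**2. What the rule does to a swab sequence.** Take central results of negative on Day 1, negative on Day 3 and positive on Day 5.
- Set: included, through Day 5.
- Literal reading: the event is Day 1 if the patient was randomized before that swab.
- Baseline reading: SAP 5.1 says "Baseline is defined as the last available assessment prior to first dose of study treatment", and the Table 2 row on RNA positivity is assessed "as measured by RT-qPCR at Day 3, Day 5, Day 7 and Day 14". The Day 1 swab is then baseline, and the event is Day 3.

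Both dates precede the first central positive. No other passage changes this.

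**3. How many patients (assumed).** Let f be the share negative on Day 1 and q the share of those who convert. The late-entrant share of an arm's set is fq/(1 − f + fq). The base case takes f = 10% and q = 50% on placebo. On active, q = 1 − (1 − 0.50)^(1/1.25) = 42.6%, in line with a hazard ratio of 1.25 for clearance.
- Placebo: 0.050/0.950 = 5.3%, or 462 × 0.050 = 23 patients.
- Active: 0.0426/0.9426 = 4.5%, or 924 × 0.0426 = 39 patients.
- Total: about 62 of 1386. About half (31) are assumed also negative on Day 3.

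**4. Power (assumed clearance curves).** The simulation uses 1386 patients, 2:1, swabs on Days 1, 3, 5, 7 and 14, an unstratified log-rank test at two-sided 0.025, and 20,000 trials per case (Monte Carlo error about 0.003). Placebo cumulative first-negative at Days 3/5/7/14 is 10/20/35/70% (mid) or 5/10/20/55% (slow). Active survival is placebo survival to the power 1.25. Late converters are first positive on Days 3/5/7/14 in 50/30/15/5%. Entries are mid / slow.

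| Day 1 negative; converting, placebo vs active | Literal | Day 1 cannot be the event | Day-1-positive set | Same, 3% lacking Day 1 result |
|---|---|---|---|---|
| 10%; 50% vs 43% | 0.705 / 0.587 | 0.776 / 0.669 | 0.806 / 0.717 | 0.791 / 0.703 |
| 10%; 50% vs 50% | 0.751 / 0.647 | 0.791 / 0.690 | 0.798 / 0.708 | 0.786 / 0.692 |
| 5%; 30% vs 25% | 0.795 / 0.690 | 0.817 / 0.716 | 0.825 / 0.730 | 0.813 / 0.717 |
| 5%; 10% vs 8% | 0.819 / 0.721 | 0.826 / 0.728 | 0.829 / 0.737 | 0.819 / 0.721 |

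Against the Day-1-positive set, the loss when Day 1 cannot be the event runs from 0.829 − 0.826 = 0.003 to 0.717 − 0.669 = 0.048. On the literal reading it runs from 0.829 − 0.819 = 0.010 to 0.717 − 0.587 = 0.130. These powers ignore gatekeeping, so operating power is lower.

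**5. Direction.** With no clearance effect and equal conversion, false superiority is 0.012-0.013 on every reading (nominal 0.0125). With no clearance effect and conversion of 43% on placebo against 50% on active, it is 0.015 (Day 1 not an event) or 0.020 (literal), against 0.012 in the restricted set. In the opposite direction, a separate exponential model on the literal reading took late entrants as 8% of the placebo set and 4% of the active set. With no clearance effect, it favoured placebo significantly in about 10% of runs.

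**The case against.** **Everyone was already positive at entry.** This is correct, and it limits the point. A reader might infer that patients are scored as ceasing before they are ever found positive. Protocol 4.1.1 rules that out. A local positive followed by central negatives and then a Day 5 positive may be intermittent detection. What remains is that the local test may be an antigen test, may be up to 72 hours old and is not part of the endpoint. It also does not make a patient who is positive on Day 5 one who ceased on Day 3.

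**The literal Day 1 reading is unlikely.** The baseline definition and the assessment days in Table 2 favour treating Day 1 as baseline. That makes the smaller loss the more relevant one, but the Day 3 error survives.

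**The scenarios are not calibrated.** This also stands. SAP 3 assumes 90% ever positive, whereas the placebo scenarios imply 95-96.5% (for example 1 − 0.10 + 0.10 × 0.50 = 95%). Matching 90% with half converting needs f = 20%, since 1 − 0.20 + 0.10 = 0.90. The loss with Day 1 not an event is then about 6-10 points. With 10% converting it is about 1 point. The tabled range is illustrative and not a bound.

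**A narrower rule would do.** Counting only a negative that follows a central positive would also stop premature dates, and it would keep late converters. It is a defensible alternative. It would still leave membership of the set dependent on swabs taken after dosing.

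**Conclusion.** The gap is in the text and is certain: neither document requires a central positive before the counted negative, and the set admits patients whose first one comes after dosing. It should be closed before unblinding.

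Its size is unknown. Under the assumed 5-10% Day 1 negative, the loss is about 0-5 points if Day 1 cannot be the event and up to about 13 points literally. Higher Day 1 negativity, or a larger imbalance between arms in late entrants, would cost more. All of this rests on assumed conversion rates and clearance curves, and on borrowing the primary endpoint's hazard ratio.

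Two stronger readings are not supported. A reader might infer that the error always works against the drug and can never favour it. That holds only if the drug does not raise late conversion, and the documents are silent on this. A reader might also infer that the primary endpoint is compromised because it uses the same set. In the base case with no drug effect, the primary Z statistic moves by −0.06 to +0.05 for late-entrant medians of 6 to 15 days, against 10 days for other patients. SAP 5.3.4.1 already reports the primary effect by baseline viral load. No extra primary sensitivity analysis is warranted on this ground.

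**What to change.** In SAP 5.4.1.5 and its Table 2 row:
- analyse efficacy-evaluable patients who are centrally RT-qPCR positive on the Day 1 pre-dose nasopharyngeal swab;
- count as cessation only a negative nasopharyngeal result after the first dose;
- keep censoring at Day 14;
- leave out patients with no Day 1 pre-dose nasopharyngeal result, as 5.4.2.5 does for a missing baseline temperature.

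No new samples and no protocol change are needed. The cost is that late converters leave this endpoint (about 62 of 1386 in the base case). So do patients lacking the Day 1 result, including any who gave only a nasal swab, which Protocol Appendix 1 permits. If 3% lack it (assumed), base-case power is 0.791 / 0.703, still above the 0.776 / 0.669 obtained when Day 1 merely cannot be the event. When late conversion is rare the change is about neutral or slightly negative (0.819 / 0.721 against 0.826 / 0.728 in the mildest case).

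The gain is therefore mainly not power: every counted event follows a central positive, and the endpoint's baseline condition is fixed before dosing. The change does not deal with a single negative followed by a later positive. The maintenance rules in SAP 5.1 are written for the efficacy endpoints with 21.5- or 43-hour durations and do not cover it.
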